4.8 Unanticipated Problem Reporting

There are other types of incidents, experiences, and outcomes that occur during the conduct of human subjects research that represent unanticipated problems but are not considered adverse events. For example, some unanticipated problems involve social or

economic harm instead of physical or psychological harm associated with adverse events. In other cases, unanticipated problems place subjects or others at increased risk of harm, but no harm occurs. If an unanticipated problem occurs that does not involve an adverse event, it will still be reported to the DSMB and the IRB under HHS regulation 45 CFR Part 46 ([Unanticipated Events HHS Policy](#)).

5. Study Outcomes

The study will have one primary outcome and three secondary outcome measures for the three specific aims. The primary outcome is change in SBP 12 months after the start of the intervention. The secondary outcomes are change in DBP 12 months after the start of the intervention, the number of medication changes as a measure of treatment intensification, and the additional cost of the intervention.

Aim 1: Determine if our intervention leads to decreases in SBP.

Our working hypothesis is that there will be greater decreases in both SBP and DBP among the pharmacist-intervention group than among controls. We will compute the change in SBP for each subject at 12 months compared to their initial SBP. The SBP readings will be collected at enrollment and at 12-months by research assistants. The primary outcome measure for Aim 1 will be the difference in mean SBP between the control and intervention groups at 12 months.

Aim 2: Determine if our intervention leads to intensification of therapy.

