Aim 1 Analysis: The analysis will be done on an intent-to-treat basis regardless of the number of reported BP readings or the number of pharmacist interactions with the participant. Our primary outcome will be a comparison of mean SBP values at 12 months. We will use linear mixed effects models (LMMs) with BP as the outcome. We will explore the timing of the change by also evaluating BP at 6 months. To test the intervention, we will include time (baseline, 6 month, 12 month) as a fixed effect factor and its interaction with treatment arm. We will use random effects for clinic and physician nested within clinic to account for practice heterogeneity between clinics and providers. Temporal correlation will be accounted for by using an autoregressive error structure. Specifically, the model will be given as

$$\begin{aligned}
 BP_{cpit} &= \tau_t + \alpha_c + \gamma_{cp} + (\omega_t + \nu_{tc} + \xi_{tcp})X_{cpi} + \epsilon_{cpit}, \\
 c &= 1, \dots, C, \quad p = 1, \dots, P_c, \quad i = 1, \dots, n_{cp}, \quad t \in \{0, 6, 12\}, \\
 (\alpha_c, \gamma_{cp})' &\stackrel{\text{iid}}{\sim} N(0, G_1), \\
 (\nu_{0c}, \nu_{6c}, \nu_{12c})' &\stackrel{\text{iid}}{\sim} N(0, G_2), \\
 (\xi_{0cp}, \xi_{6cp}, \xi_{12cp})' &\stackrel{\text{iid}}{\sim} N(0, G_3), \\
 (\epsilon_{cpio}, \epsilon_{cpis}, \epsilon_{cpis})' &\stackrel{\text{iid}}{\sim} N(0, R),
 \end{aligned}$$

where C is the number of clinics, P_c is the number of providers within the c^{th} clinic, n_{cp} is the number of subjects recruited under the p^{th} provider in the c^{th} clinic, $BP_{(cpit)}$ is the blood pressure at time t for the i^{th} subject under the p^{th} provider within clinic c , τ_t is the control mean at time t , α_c and γ_{cp} are the random control effects for the clinic and provider-nested-within-clinic respectively, ω_t is the treatment effect at time t , ν_{tc} and ξ_{tcp} are the random treatment effects for the clinic and provider-nested-within-clinic respectively, X_{cpi} equals 1 if the i^{th} subject under the p^{th} provider within clinic c is assigned to the treatment group and zero otherwise, ϵ_{cpit} is the (auto-correlated) noise term, and G_1 , G_2 , G_3 , and R are covariance matrices for the random effects. This model will also be estimated for DBP.

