Second, transition to control for patients who were uncontrolled at their baseline visit will be modeled using a generalized linear mixed effects model (GLMM) based on the Bernoulli distribution with a logistic link. We will test the intervention by including a fixed-effects term for the treatment assignment (intervention versus control). As before, we will include random effects for provider nested within clinic. Specifically, the model will be

$$\begin{aligned}
 \text{logit}(\mathbb{P}(Z_{cpio} = 1 | Z_{cpis} = 0)) &= \tau + \alpha_c + \gamma_{cp} + (\omega + \nu_c + \xi_{cp})X_{cpi}, \\
 (\alpha_c, \gamma_{cp})' &\stackrel{\text{iid}}{\sim} N(0, G_1), \\
 (\nu_c, \xi_{cp})' &\stackrel{\text{iid}}{\sim} N(0, G_2),
 \end{aligned}$$

where Z_{it} equals 1 if the i^{th} subject under the p^{th} provider within clinic c is controlled at time t , $t \in \{0, 6\}$, and zero otherwise.

Third, we will assess the duration of the change by modeling the odds of having controlled BP at 12 months among those uncontrolled at baseline but controlled at 6 months using a GLMM similar to that described above. All three models will contain any covariates (e.g., age, sex) that were not sufficiently addressed through randomization. In all analyses, the random effects incorporated into the final model will be chosen via Akaike Information Criterion with correction for small sample sizes (AICc).

Power: Based on prior work with the CAPTION trial, we expect a mean decrease in SBP of 17.3 (SD = 17.7) mmHg in the intervention arm and a decrease of 11.6 (SD = 18.2) mmHg in the control arm. We expect a difference of 5.65 mmHg between the groups with an expected pooled standard deviation of 17.9 with equal sized groups. In order to have 90% power to detect a difference of 5.7 mmHg or larger decrease in SBP with a Type I error rate of 5% and a standard deviation of 17.9 mmHg, we would need 180 subjects per arm or 360 subjects total.

In preliminary work in the CAPTION trial, 13.4% of control subjects dropped out or were lost to follow-up. 14.0% of subjects dropped out of the intervention arm during the first 9 months. In order to retain power after reasonable attrition rates over 12 months, we will recruit an additional 14% in each group to ensure we have at least 85% power. In addition, the sample size should be slightly increased to accommodate the interim analyses. This increases our total sample size to 420.

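### The plan never fixes the primary SBP contrast, and its model estimates a pre-randomization arm difference instead of adjusting for baseline SBP

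*Combined protocol and SAP*

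**What the plan says.** **Level at 12 months.** The synopsis, the Aim 1 hypotheses in Section 2.2 and Section 6 all describe the primary comparison as SBP level. Section 6 puts it as "Our primary outcome will be a comparison of mean SBP values at 12 months". Section 5 closes its Aim 1 paragraph the same way: "The primary outcome measure for Aim 1 will be the difference in mean SBP between the control and intervention groups at 12 months".

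**Change.** Section 5 opens with "The primary outcome is change in SBP 12 months after the start of the intervention" and adds "We will compute the change in SBP for each subject at 12 months compared to their initial SBP". The power inputs, in the synopsis and in Section 6, are mean decreases and their SDs: 17.3 (SD 17.7) against 11.6 (SD 18.2) mmHg, pooled SD 17.9.

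**Model.** The synopsis describes a model with 12-month BP as the outcome. Section 6 gives a three-occasion model (t = 0, 6, 12): "To test the intervention, we will include time (baseline, 6 month, 12 month) as a fixed effect factor and its interaction with treatment arm". Its parameter ω_t "is the treatment effect at time t", so ω₀ is estimated, together with random treatment effects at baseline for clinic (ν₀c) and provider (ξ₀cp).

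**Covariates and model selection.** "All three models will contain any covariates (e.g., age, sex) that were not sufficiently addressed through randomization". Separately, "the random effects incorporated into the final model will be chosen via Akaike Information Criterion" with a small-sample correction.

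**Timing.** Section 4.1 and Appendix 2 place the baseline visit on Day 0 and randomization after the home BP period, between Days 7 and 18.

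**The concern.** Three things do not fit together.

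1. The tested parameter is not named. An analyst who follows the level wording tests ω₁₂. One who follows the change wording, or who reads the time-by-arm interaction in the usual way, tests ω₁₂ − ω₀. Both estimate the same effect under randomization, but they can give different p-values, and the choice remains open.
2. Baseline SBP precedes randomization, so ω₀ is zero by design. Leaving it free discards that knowledge. With complete, balanced data, ω₁₂ then makes no use of baseline SBP.
3. Nothing else reliably brings baseline SBP in. The covariate rule depends on observed imbalance and does not name it. The AICc step may remove ν₀c and ξ₀cp, but it covers random effects only, so the fixed effect ω₀ stays.

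At stake are the precision of the primary estimate and the assurance that 180 completers per arm are enough for the test actually run.

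**Working it through.** **Inputs from the plan:** SD of change 17.9; difference 5.65 mmHg (5.7 in the following sentence); 180 per arm at 12 months; 420 enrolled; 14% attrition; type I error 5%. **Assumed:** two-sided test; equal SDs at baseline and 12 months; correlation ρ between them of 0.3, 0.5 or 0.7.

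**Step 1: the plan's own figure.** For a two-sample t-test with SD 17.9 and 180 per arm, power is 84.8% at 5.65 and 85.4% at 5.7 mmHg. At 5.7, 85% power needs 179 per arm, so the synopsis figure reproduces. The 90% that Section 6 gives for the same 180 does not: it needs 209. Attrition: 360/(1 − 0.14) = 419, which agrees with 420. The trial is therefore sized for the change contrast.

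**Step 2: power by contrast.** Var(change) = 2σ²(1 − ρ), so σ = 17.9/√(2(1 − ρ)). The baseline-adjusted SD is σ√(1 − ρ²).

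| ρ | σ | Power, change | Power, ω₁₂ (ω₀ free) | Adjusted SD | Power, adjusted |
|---|---|---|---|---|---|
| 0.3 | 15.1 | 85% | 94% | 14.4 | 96% |
| 0.5 | 17.9 | 85% | 85% | 15.5 | 93% |
| 0.7 | 23.1 | 85% | 64% | 16.5 | 90% |

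(180 per arm, 5.65 mmHg.) Power for ω₁₂ equals the change-scale figure only at ρ = 0.5; it is higher below that and lower above it.

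**Step 3: cost in patients.** Adjustment removes ρ² of the variance of ω₁₂: 9%, 25%, 49%. To match it without adjustment would take 180/(1 − ρ²) = 198, 240 or 353 completers per arm.

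**Step 4: does the mixed model recover this by itself?** Generalized least squares on the three visits (AR(1), equal SDs, no cluster effects), with values in the order ρ = 0.3, 0.5, 0.7:

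| Data per arm | Var(ω₁₂), ω₀ free | Var(ω₁₂), ω₀ = 0 | Ratio |
|---|---|---|---|
| 180 complete | 2.54, 3.56, 5.93 | 2.31, 2.67, 3.03 | 0.91, 0.75, 0.51 |
| 210, of whom 30 have baseline only | 2.51, 3.43, 5.52 | 2.31, 2.67, 3.03 | 0.92, 0.78, 0.55 |
| 210, of whom 30 have baseline and 6 months | 2.43, 3.31, 5.34 | 2.24, 2.54, 2.85 | 0.92, 0.77, 0.53 |

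Var(ω₁₂ − ω₀) with complete data is 2 × 17.9²/180 = 3.56 at every ρ. With the planned attrition the free-ω₀ model gains only 1%, 4%, 7% (dropouts with baseline only) or 4%, 7%, 10% (dropouts with 6-month SBP too) for ω₁₂. Most of the loss remains.

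**Step 5: clustering.** Assume 4 clinics × 5 providers × 18 patients, arms balanced, and clinic and provider intercept variances of 4 each. The ratio stays at 0.91, 0.75, 0.51. Adding random treatment effects (variance 2 each, uncorrelated over time) gives 0.94, 0.82, 0.60 with ν₀c and ξ₀cp kept, and 0.93, 0.79, 0.55 with them removed.

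**Step 6: narrower baseline.** Enrolment selects on raised BP, so take a baseline SD of 12 and keep the SD of change at 17.9. At ρ = 0.3 and 0.5 the 12-month SD is 17.4 and 20.6. Power for ω₁₂ is 87% and 74%; with adjustment it is 90% and 85%. The variance saved against the change score is 14% and 1%, compared with 35%, 25%, 15% at ρ = 0.3, 0.5, 0.7 under equal SDs. ρ = 0.7 is left out here because it implies a regression slope of 1.41 on baseline.

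**The case against.** The strongest reply is that each reading, taken alone, is coherent. On the level reading, Section 6 names the 12-month comparison and defines ω_t, so ω₁₂ follows even if the symbol is not singled out. On the change reading, the interaction sentence, the change wording in Section 5 and the power inputs agree, and 85% power is verified. A repeated-measures model with a free baseline is also valid, so preferring adjustment is a choice about efficiency. The documents give neither the correlation nor the visit SDs. Below ρ = 0.5 with equal SDs the plan exceeds its own 85%. Selection on raised BP (Section 3.1 and the baseline form in Appendix 5) tends to narrow baseline SBP, and random treatment effects shrink the saving.

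Much of this stands as a limit on size. The ρ = 0.7 row needs an SD of 23.1 at both visits and is an upper end. Against the change score the benefit may be negligible. The 85% and 90% discrepancy is a separate error and adds no weight here.

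It does not remove the point. Two coherent readings with different tests are exactly what a primary analysis must not leave open. Whichever is chosen, the adjusted estimate is in large samples at least as precise. A narrower baseline does not rescue ω₁₂ either: its power is 74% at ρ = 0.5. Baseline SBP being a response already does not help while ω₀ is free.

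**Conclusion.** The point holds. The primary contrast is incompletely specified, and the model as written gives up precision by estimating an effect known to be zero. There is no bias: ω₁₂, ω₁₂ − ω₀ and the adjusted difference share the same expectation under randomization with complete data.

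The firm gain is over ω₁₂: 9% to 49% of its variance for ρ from 0.3 to 0.7 with equal SDs, 8% to 47% with the planned attrition, and 6% to 45% with the assumed random treatment effects. The gain over the change score ranges from about 1% to 35% in the cases tried. These sizes rest on assumed correlations, SDs and cluster variances. That power for ω₁₂ is unverified, and that the contrast is not named, rest on the documents alone. This should be corrected, but it does not invalidate the trial.

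**What to change.** Before unblinding, state one primary contrast: the between-arm difference in mean SBP at 12 months, adjusted for baseline SBP. Two equivalent routes are open:

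- model 6- and 12-month SBP with baseline SBP as a prespecified covariate, and test the 12-month arm effect; or
- keep baseline in the outcome vector with ω₀ = 0 and without ν₀c and ξ₀cp, and test ω₁₂.

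Do the same for DBP, and take baseline BP out of the imbalance-triggered covariate rule. Bring the synopsis, Section 5 and Section 6 into line with the chosen contrast, and say in the power paragraph that 17.9 is an SD of change.

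The cost is wording in the analysis plan. Baseline SBP is already collected, so no patients, visits or procedures are added.

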Statistical Design and Power	
The analysis will be done on an intent-to-treat basis regardless of the number of reported BP readings or the number of pharmacist interactions with the participant.
 
Our primary outcome will be a comparison of mean SBP values at 12 months. We will use a linear mixed effects model with mean BP at 12 months as the outcome. We will use random effects for clinic and physician nested within clinic to account for practice heterogeneity between clinics and providers.
 
Based on prior work with the CAPTION trial, we expect a mean decrease in SBP of 17.3 (SD = 17.7) mmHg in the intervention arm and a decrease of 11.6 (SD = 18.2) mmHg in the control arm. We expect a difference of 5.65 mmHg between the groups with an expected pooled standard deviation of 17.9 with equal sized groups. In order to have 85% power to detect a difference of 5.7 mmHg or larger decrease in SBP with a Type I error rate of 5% and a standard deviation of 17.9 mmHg, we would need 180 subjects per arm or 360 subjects total.
 
In preliminary work in the CAPTION trial, 13.4% of control subjects dropped out or were lost to follow-up. 14.0% of subjects dropped out of the intervention arm during the first 9 months. In order to retain power after reasonable attrition rates over 12 months, we will recruit an additional 14% in each group to ensure we have at least 85% power. In addition, the sample size should slightly increase to accommodate the interim analyses. This increases our total sample size to 420.
 
One interim analysis is planned after outcome data is received and the results are reported to the Data Safety and Monitoring Board from the first half of the study. The interim monitoring method of Lan and DeMets will be used with O'Brien-Fleming alpha spending function for the interim analyses. Accordingly, type I error rate of 0.00305 for the interim analysis and 0.4695 will be used for the final analyses. The current sample size of 420 patients total accommodates the interim analyses.

Futility Analysis	To be determined by the Data and Safety Monitoring Board

Table of Contents

Study Protocol.....	1
Protocol Approval Page	2
Protocol Version and Amendment Tracking	3
Protocol Synopsis	4
Table of Contents.....	6
Table of Appendices	7
Abbreviations	8
1. Introduction.....	9
1.1 Background.....	9
1.2 Clinical Experience with the Study Intervention	9
2. Objectives, Aims, and Hypotheses	10
2.1 Objective.....	10
2.2 Aims and Hypotheses	10

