3.1 Inclusion Criteria

- English or Spanish speaking males and females.
- 21 – 100 years of age.

- Clinic measured blood pressure of ≥ 145 mmHg or ≥ 95 mmHg at two previous clinic visits or one previous clinic visit and on the day of enrollment. Previous clinic visit BPs must be within the past 18 months and measured at least 2 weeks apart from each other.
- Lives in a zip code that is scored as a 4-10 on the Rural-Urban Commuting Area (RUCA) Codes.

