Appendix 5: Baseline REDCap Form

Page 1

Baseline Data

Record ID _____

Date of Baseline Measures _____

Research Blood Pressure Measurements:

--Prepare the Participant--

- *No smoking 20 minutes prior to BP measurement
- *Remove all clothing that covers the location of cuff placement
- * Sit comfortably in a chair, with back supported, legs uncrossed and flat on floor, arm supported at level of the heart on table, palm facing upward
- *Sit for at least 5 minutes before first measurement; relax as much as possible

--Cuff Measurement--

- * Choose cuff that fits arm circumference you previously measured. If arm measurement falls on number that is specified for 2 cuffs, both cuffs should be placed on arm sequentially and the cuff for which the INDEX arrow that is marked on the cuff best falls within the range bar should be chosen

--Cuff Placement--

- *Do not allow a sleeve to form a tourniquet on the arm
- *Palpate the brachial artery in the antecubital fossa and place the ART arrow that is marked on the midline of the bladder of the cuff so that it is over the arterial pulsation of the participant's bare arm
- * The lower end of the cuff should be 1/2 to 1 inch above the inner side of the elbow joint
- *The middle of the cuff should be at the level of the right atrium
- * Place the cuff snugly around the bare upper arm so that you can only insert one finger between the cuff and the arm

--BP Measurement--

- *Use the Omron HEB-907-XL
- *Tell the participant you will be taking 3-4 measurements and that neither of you should talk during the measurement time
- *Take first measurement and record (this value will be ignored). Wait 60 seconds before taking next measurement
- *Take second measurement and record. Wait 60 seconds before taking next measurement
- *Take third measurement and record. If 2nd and 3rd values are more than 4 mmHg apart, take a 4th reading.
- *The two nearest values (of 2-4) will be averaged. If the average value is less than 145 or 95, the person NOT eligible to continue with the study. Thank them for their time.

If you get an error message at any point, start the sequence over!

1st Blood Pressure (this value is ignored)

Baseline SBP #1

Baseline DBP #1

2nd Blood Pressure

Baseline SBP #2

Baseline DBP #2

(If average BP value is less than 145 or 95, the patient is NOT eligible.)

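### If the planned autoregressive error structure is the usual one-variance form, the 12-month SBP difference may get too small a standard error; an unstructured covariance removes the risk

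*Combined protocol and SAP*

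**What the plan says.** **Model.** In the Aim 1 analysis of section 6, "we will include time (baseline, 6 month, 12 month) as a fixed effect factor and its interaction with treatment arm". Each of the three visits has its own control mean and its own treatment effect. Random effects are for clinic and for physician within clinic; there is none for the participant. Within-participant correlation is left to the residual term: "Temporal correlation will be accounted for by using an autoregressive error structure". The residual matrix R appears only as a symbol, in the list ending "and R are covariance matrices for the random effects". Neither the order of the autoregression nor equal or unequal visit variances are stated. No robust standard error, degrees-of-freedom method or fallback is given. AICc selection is planned for the random effects.

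**Contrast.** Section 6 says "Our primary outcome will be a comparison of mean SBP values at 12 months". Section 5 says "The primary outcome is change in SBP 12 months after the start of the intervention", and then names the 12-month difference in means as the Aim 1 measure. The synopsis describes a different model: "We will use a linear mixed effects model with mean BP at 12 months as the outcome".

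**Entry.** Sections 3.1 and 4.2 accept elevated clinic BP, systolic or diastolic, "at two previous clinic visits or one previous clinic visit and on the day of enrollment". The baseline form in Appendix 5 says of the research reading: "If the average value is less than 145 or 95, the person NOT eligible to continue with the study".

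**The concern.** In its usual form AR(1) has two parameters: one variance shared by all visits and one correlation, with the 0-to-12-month correlation equal to the square of the 6-month one. Here baseline is one of the outcomes, and participants enter because their BP is high. If that selection makes baseline SBP less variable than follow-up SBP, the single variance is a compromise, too large for baseline and too small for 12 months. With no participant random effect and no visit-specific variance, nothing else in the stated model clearly corrects this.

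At stake is the standard error of the primary comparison. For the 12-month difference it would be too small, and the test would reject a true null too often. For change from baseline the error tends to go the other way.

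**Working it through.** **1. The plan's own figure.** With a difference of 5.7, SD 17.9, two-sided 5% (sidedness assumed) and 85% power, n per arm = 2 × (17.9/5.7)² × (1.960 + 1.036)² ≈ 177, or 178 with rounding in the method used, against the stated 180. Then 180/0.86 = 209.3, so 210 per arm and 420 in total. The sample size reproduces at 85% power. It rests on the SD of *change* (17.7 and 18.2, pooled 17.9). The documents give no SD at baseline, 6 or 12 months, no visit correlation, and no type I error for this model, so the visit SDs below are assumptions.

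**2. Consistency with 17.9.** The implied correlation is r = (s0² + s12² − 17.9²)/(2·s0·s12). With s12 = 17, a baseline SD of 10 gives (100 + 289 − 320.41)/340 = 0.20, and 14 gives (196 + 289 − 320.41)/476 = 0.35. Both are possible values, so the plan's figure does not settle the baseline SD.

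**3. What one-variance AR(1) does to the 12-month test.** To a close approximation the fitted variance is the mean of the visit variances, weighted by observations. Take 14% dropout, half before 6 months and half before 12 (assumed), giving weights 1, 0.93 and 0.86:

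σ² ≈ (s0² + 0.93·s6² + 0.86·s12²)/2.79; SE ratio ≈ σ/s12; type I error ≈ 2 × [1 − Φ(1.96 × SE ratio)].

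For SDs 10/16/17: (100 + 238.08 + 248.54)/2.79 = 210.3, σ = 14.50, ratio 14.50/17 = 0.853, and 2 × [1 − Φ(1.672)] = 9.5%.

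| SD at 0/6/12 months | σ² | SE ratio | Type I error, formula | Limiting AR(1) fit, several correlation patterns |
|---|---|---|---|---|
| 10/16/17 | 210.3 | 0.85 | 9.5% | 9.5–9.7% |
| 12/16/17 | 226.0 | 0.88 | 8.3% | 8.3–8.5% |
| 14/16/17 | 244.7 | 0.92 | 7.1% | 7.0–7.2% |
| 15/16/17 | 255.1 | 0.94 | 6.6% | 6.4–6.6% |
| equal | – | 1.00 | 5.0% | about 5% |

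**4. Simulation under the null.** 210 per arm, 14% dropout, REML AR(1), 3,000 runs per row, with the 6-month SD set equal to the 12-month SD. Monte Carlo standard error is about 0.4 points near 5%, slightly more for the larger rates.

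| SD at 0 and 12 months | AR(1), 12-month difference | AR(1), change | 12-month comparison with its own variance |
|---|---|---|---|
| 8, 17 | 10.4% | 3.7% | 5.7% |
| 10, 17 | 8.0% | 3.4% | 4.4% |
| 11, 16.5 | 8.5% | 3.5% | 5.2% |
| 10.8, 15.4 | 8.1% | 2.8% | 5.0% |
| 13.6, 15.4 | 6.0% | 2.9% | 5.0% |
| 15.6, 15.7 | 4.2% | 3.7% | 4.8% |

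In a separate run of 1,500 trials at SDs 8 and 17, AR(1) gave 10.7%, heterogeneous-variance AR(1) 6.2% and unstructured R 5.7%.

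**5. Which SD ratio the entry rules produce.** Selection simulated in assumed populations gave these baseline-to-12-month SD ratios:
- Research baseline must qualify (Appendix 5): 0.65–0.80, type I error 7.1–8.1% in the cases computed.
- Any route in section 3.1: about 0.88–0.91, about 6%.
- Two earlier visits only: 1.00, about 5%.

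All these checks omit the clinic and physician random effects.

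**The case against.** A reader might infer that the plan fixes one variance for all visits and so commits itself to a type I error of 8–10%. The documents do not support that, for four reasons.

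- **Equal variances are not stated.** R is a general symbol, and a heterogeneous autoregressive structure fits the same words. This stands, and it makes the point conditional. It does not remove it: the text ties R to an autoregressive form, the one-variance version is the usual reading, and an analyst could follow the plan to the letter and fit it. The AICc step concerns which random effects are included, and does not clearly reach R.
- **Truncation of baseline is not settled.** Under sections 3.1 and 4.2 two earlier visits suffice, so the research baseline need not be elevated. Because systolic or diastolic elevation qualifies, SBP is not cut cleanly at 145. Only the baseline form requires the research average to qualify. This stands: under mixed entry the inflation is about one point.
- **The contrast and model are not settled.** Change from baseline is also named as primary, and the sample size uses SDs of change. For that contrast AR(1) is mostly conservative. The synopsis's 12-month-only model has no baseline variance to pool. Both points stand. They also mean that the same R errs in different directions depending on which statement is followed.
- **The checks do not fit the full model.** Visit-specific random treatment effects might absorb a little of the heterogeneity in the intervention arm. How much is unknown.

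**Conclusion.** The concern holds conditionally. If section 6 is carried out with a one-variance AR(1), and the 12-month difference is tested, narrowing of baseline SBP makes its standard error too small. With 12-month SD 17 and 6-month SD 16, the shortfall is about 6–8% at a baseline SD of 14–15 (type I error 6–7%), about 12% at 12 (about 8%) and about 15% at 10 (between 9 and 10%). With equal SDs there is no inflation. The upper end needs a baseline SD of roughly 0.6 of the 12-month SD or less.

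For change from baseline the structure is mostly conservative, about 3–5%, which costs power rather than validity. These figures rest on assumed visit SDs and correlations, 14% dropout, a nominal two-sided 5%, and no clinic or physician effects. They show the direction and plausible size of the problem; they do not estimate this trial's error rate. The change is worth making because it protects either contrast at almost no cost.

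**What to change.** In section 6, replace the autoregressive structure with an unstructured 3×3 within-participant covariance for baseline, 6 and 12 months, with Kenward-Roger or Satterthwaite degrees of freedom. Name a heterogeneous-variance structure, such as heterogeneous Toeplitz, as the fallback if the model does not converge. State one primary model and one primary contrast, in the same words, in the synopsis, section 5 and section 6. Reconcile the BP entry rule in sections 3.1 and 4.2 with the baseline form in Appendix 5, since it determines how far baseline SBP is narrowed.

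Cost: a few sentences. The unstructured matrix has six parameters against two for one-variance AR(1), so four more, which is negligible with 420 participants and three visits.

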The pharmacists will review the home BP values with the intervention subjects. If the home BP values are controlled, the pharmacist will continue to monitor home BP values.

However, if the pharmacist identifies issues such as poor medication adherence, inability to afford medications or other issues, they will work with the patient and physician to optimize therapy and/or reduce cost. If the pharmacist suspects white coat hypertension, they will make a recommendation to the physician to refer the patient to the University of Iowa ambulatory blood pressure service.

If BP values are elevated, the pharmacist will assess medication adherence, ability to pay for medications and whether the regimen is optimal to control BP based on patient demographics and co-existing conditions. The pharmacist will communicate recommendations for lifestyle and other changes directly to the subject. If medication changes are needed, the pharmacist will communicate to the physician through the electronic medical record. The pharmacist may recommend:

1. Increased dose of a medication.
2. Addition of a medication.
3. Discontinuation of a medication.
4. Modification of the regimen to optimize therapy, improve convenience (e.g. fixed-dose combinations) or reduce cost.

All participants in the pharmacist intervention group will continue to have access to a research pharmacist for the entire 12 months of follow up. Additionally, they will be asked to continue measuring and texting BP values (1 morning, 1 evening) for 3 days each month throughout the 12-month follow up.

The pharmacists will typically contact with the participants every 2 weeks while BP is not controlled. Once BP is controlled, they will continue monitoring the participant's records and home BPs and make contact at least every 2 months to support adherence and reassess BP control.

The REDCap forms that the pharmacists will use to record data are shown in Appendix 10

4.5 6-Month Visit Procedures

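### No planned model compares blood pressure control at 12 months between arms in all randomised participants uncontrolled at baseline

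*Combined protocol and SAP*

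**What the plan says.** The Aim 1 Analysis in section 6 has three models. The first is a linear mixed model for blood pressure at 0, 6 and 12 months, fitted to SBP and again to DBP. The other two concern control.

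- **Second model.** The plan states that "transition to control for patients who were uncontrolled at their baseline visit will be modeled using a generalized linear mixed effects model". Its indicator equals 1 if the participant "is controlled at time t , $t \in \{0, 6\}$, and zero otherwise".
- **Third model.** The duration of the change is assessed through "the odds of having controlled BP at 12 months among those uncontrolled at baseline but controlled at 6 months".

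The section then refers to "All three models will contain any covariates (e.g., age, sex) that were not sufficiently addressed through randomization", so there is no fourth model.

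On timing, section 6 says: "Our primary outcome will be a comparison of mean SBP values at 12 months". Section 5 agrees: "The primary outcome is change in SBP 12 months after the start of the intervention". Section 4.6 has research blood pressure measured at the 12-month visit in all participants. Under section 4.4.2, intervention participants "continue to have access to a research pharmacist for the entire 12 months of follow up".

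**The concern.** The control analyses stop short of the trial's main time point. A reader of the results will want to know what proportion of each arm was controlled at 12 months, among those who were not controlled at the start. The plan, followed exactly, does not produce that comparison.

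The only control contrast at 12 months is restricted to participants controlled at 6 months. That restriction is itself an outcome of randomised treatment, so the two arms in that subset are no longer comparable by randomisation. If the analysis is added after the arms have been compared, it will be post hoc.

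**Working it through.** The plan gives no control rate, effect size or power for either control model, so there is no figure of its own to reproduce. The check is structural, followed by an illustration.

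**1. Follow the possible paths.** Take participants uncontrolled at baseline, with all visits attended.

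| Month 6 | Month 12 | Second model | Third model |
|---|---|---|---|
| controlled | controlled | event | event |
| controlled | not controlled | event | non-event |
| not controlled | controlled | non-event | not included |
| not controlled | not controlled | non-event | not included |

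The last two rows are identical to both control models, although they differ in status at 12 months.

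A participant whose 6-month visit falls after the 5-to-7-month window has a missing 6-month outcome (section 4.5). Without imputation, which section 6 does not mention, that participant contributes to neither control model, even with a valid 12-month reading.

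**2. Why the 12-month rate cannot be rebuilt.** Among those uncontrolled at baseline, let c6 be the proportion controlled at 6 months, s the share of these still controlled at 12 months, and l the share of the remainder controlled at 12 months. Then

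12-month control = c6 × s + (1 − c6) × l.

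The second model informs c6 and the third informs s. Nothing informs l.

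**3. Illustration.** All values of c6, s and l are assumptions.

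- *Benefit missed.* c6 = 40% and s = 85% in both arms; l = 30% (intervention) and 10% (control). Intervention: 0.40 × 0.85 + 0.60 × 0.30 = 0.34 + 0.18 = 52%. Control: 0.34 + 0.60 × 0.10 = 40%. Both planned control models show no difference; the 12-month difference is 12 points.
- *Benefit that fades.* c6 = 50% and 40%, s = 85% in both, l = 10% and 20%. Intervention: 0.425 + 0.05 = 47.5%. Control: 0.34 + 0.12 = 46.0%. The second model shows a 10-point gain; the 12-month difference is 1.5 points.

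With c6 from 30% to 50% and l from 10% to 30%, the unseen term (1 − c6) × l runs from 0.50 × 0.10 = 5% to 0.70 × 0.30 = 21% of those uncontrolled at baseline.

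**4. Does the choice of visit affect power?** A simulation used the plan's figures (mean SBP fall 11.6 mmHg in control, 5.7 mmHg more with intervention at 12 months, SD of change 17.9, 180 analysed per arm). It assumed a mean baseline of 152, an SD of usual SBP of 12, a single-visit within-person SD of 10, a correlation of 0.7 between true changes at 6 and 12 months, and a cut-off of 140 used only for illustration. Power is for a two-sided 5% comparison of proportions.

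| Share of effect present at 6 months | Power at 6 months | Power at 12 months |
|---|---|---|
| all | about 56% | about 56% |
| three quarters | 33–35% | 55–56% |
| half | 18–19% | 54–56% |

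Power differs between the visits only if the effect is still building at month 6.

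**The case against.** The strongest reply is that little is lost. Control is not among the one primary and three secondary outcomes in section 5 and has no power statement. The primary mixed model uses every 12-month SBP, including that of someone who first reaches control after month 6. Six months is a stated hypothesis time point (section 2.2.1), and the two control models form a deliberate sequence: reach control, then keep it. All of this stands, and it limits the weight of the point. It does not supply the missing 12-month comparison.

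A reader might go further and infer that the second model misclassifies late responders. It does not. Someone uncontrolled at 6 months is correctly a non-event for a 6-month outcome.

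A reader might also take simulated late transitions as a count of late responders. In the simulation above with the full effect at 6 months, about 15% of those uncontrolled at baseline are uncontrolled at 6 and controlled at 12 months. But about 15% move the other way, only about 28% of the late cases cross the cut-off in true pressure, and 12–13% remain when true pressure does not change between visits. Most of it is reading-to-reading variation.

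Nor do the documents support a claim that power is lost. They neither state nor exclude an effect still building at 6 months. Section 4.4.2 speaks of improving control quickly, with contact typically every 2 weeks while pressure is uncontrolled, which if anything suggests early action.

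**Conclusion.** The point holds as a gap in the supporting analyses. The plan contains no randomised comparison of control at its own primary time point, and its two control models cannot be combined to give one. This follows from the definitions alone.

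The possible size depends on assumed rates. In the illustrations, a 12-point difference at 12 months goes unseen in one case, and a 10-point gain at 6 months shrinks to 1.5 points in the other, so the control results could mislead in either direction. Any loss of power is conditional on an effect still building at 6 months. The SBP and DBP mixed model is unaffected, and the 6-month control model is sound for what it estimates. The change should be made, but the trial's main conclusion does not depend on it.

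**What to change.** In the second Aim 1 model, define the control indicator at 0, 6 and 12 months. Fit the same GLMM to control at 12 months in all randomised participants uncontrolled at baseline, and name it as the control analysis that matches the primary time point. Keep the 6-month fit for timing. Label the model restricted to participants controlled at 6 months as descriptive. Section 6 gives no cut-off for controlled blood pressure, so the text should state the definition that all these models use.

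The cost is a short change of wording and one more fit of a model already planned. Missing data will probably be somewhat greater at 12 months than at 6. Visits, sample size and the primary SBP test do not change. The change should be made before outcomes are compared by arm.
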